a) General Cognitive: American National Reading Test (AMNART) for estimated IQ.⁴⁶ This test is chosen to determine if changes from treatment could be associated with IQ and to compare groups that may have differential responses to treatment.

b) Attention and Cognitive Flexibility: Trail Making Test parts A and B⁴⁷; Color Word Interference Test.³⁶

1. For Trails A and B, Trails A measures processing speed and simple attention, and Trails B utilizes the same cognitive components as Trails A with the additional executive function of alternating sequencing. This test is not a direct measure of retrieval but is used to assess for generalization or indirect improvement with HD tDCS. Test-retest reliability is reported as r = 0.745 for Trails A, r = .849 for Trails B, and r = .971 for B-A.⁴⁸

2. Delis-Kaplan Color Word Interference Test³⁶ measures processing speed in the control conditions of color naming and word reading with color word names written in a different ink color than the name measures inhibitory control, an executive function. This test is not a direct measure of retrieval but is used to assess for generalization with HD tDCS, particularly to compare to performance on the inhibitory aspects of the Semantic Selection Tasks. Internal consistency is reported as Cohen's alpha = .62-.86 over age groups from 9 to 89 years of age (Manual), and within in the age GWV, Cohen's alpha = .72-.86. Test-retest reliability is reported as Color Naming r = .76, Word Reading, r = .62, Inhibition r = .75, and Inhibition/Selection r = .65, with lower test-retest reliability coefficients for 50-89 year olds, r = .50-.57.³⁶

3. Digit Span Forwards and Backwards⁴⁹ measures simple attention with digit span forwards and working memory with digit span backwards. This is chosen not because it is to be directly affected by the HD tDCS, but to determine that verbal episodic memory increases are from improvements in attention (digits forward) and to determine if there is generalization to working memory (digits backward). Test-retest reliability coefficients for Digits forwards ranges from .66-.89 and Digits Backwards approximating 0.70.⁵⁰

c) Visual Memory: Rey-Osterrieth Complex Figure Test (Copy and Memory components)⁵¹ The task requires a subject to copy a complex geometric figure and then later to draw what aspects of the figure that they

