still remember. It is included in this study as a check to determine if retrieval improvement is not only in verbal retrieval but also generalizes to nonverbal material retrieval. Reliability across alternate forms is reported as Copy r = .50, Immediate Recall r = .76, and Delayed Recall r = .69, and reliability over one year is Copy r = .18, Immediate Recall r = .47, and Delayed Recall r = .592.⁵²

d) Psychomotor Speed: Grooved Pegboard Test. This test of psychomotor speed utilizes placement of pegs into slots of varying orientations. It is included to assess the specificity of tDCS to retrieval versus generalization to processing speed and the possibility that improved processing speed might mediate improved retrieval. The test has good test-retest reliability (0.91 and 0.85 for right and left hands, respectively).^{53, 54}

e) Beck Depression Inventory.⁵⁵ (Beck et al., 1996) is a subjective questionnaire of depressive symptomatology. The test is not being used as a marker of retrieval, but to determine if mood improvement that may be secondary to HD tDCS application may be accounting for minor improvements in retrieval.⁵⁴ Cronbach's average alpha coefficient average around 0.9, ranging from 0.83to 0.96, test-retest reliability ranges between 0.73 to 0.96.^{56, 57}

2. EEG Tasks

a. Semantic Object Retrieval Test (EEG version).³³ The stimuli in this EEG paradigm comprise 112 pairs of words. There are 56 retrieval and 56 nonretrieval word pairs. The "retrieval" and "non-retrieval" attributes of the word pairs have been validated in previous studies with different groups of subjects. Words will be presented simultaneously one pair at a time for three seconds, with one word above the other. Between trials, a + sign will be presented for three seconds as a visual fixation target. Participants will be instructed to respond "yes" or "no" depending on whether they could think of any particular object upon seeing each word pair. Word stimuli will be presented on an LCD screen placed about 46 inches from the eyes using Stim2 software (Compumedics Neuroscan, USA). Responses will be made by pressing a button under the right index finger for *no*. The entire task lasts about 11 minutes. The retrieval trials index successful access to an object memory represent-ation including verbal information, with the correct nonretrievals indicating a memory search that leads to a conclusion that the features do not combine to activate an object memory.

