The efficacy of HD tDCS will be assessed on each outcome. For the cognitive-behavioral measures (i.e., from SORT, COWA, BNT, CVLT, Trails A & B, Color Word Interference, Digits Forward & Backward, Rey-Osterrieth Complex Figures Test, Grooved Pegboard Test, and Beck Depression Inventory), a mixed-model MANOVA initially will be used to test for omnibus group (active vs sham) effects over time (i.e., Group X Time interaction effects). Given a significant multivariate effect, separate univariate mixed-model ANOVAs for each cognitive-behavioral measure will be evaluated for group (active vs sham) effects over time, and significant interaction effects will be followed up by separate pre- versus post-intervention evaluations for each tDCS group. Verbal fluency has been associated with sex, age, and education^{70, 71 but see 72}; thus, these variables will be included in the models. Additionally, potential mediating effects of IQ (based on NAART) and pre-test to post-test change in executive function, simple attention, working memory, processing speed, and depression (measured via Trails A & B, Color Word Interference, Digits Forward & Backward, Rey-Osterrieth Complex Figures Test, Grooved Pegboard Test, and Beck Depression Inventory) will be explored through covariate mediation modeling. For all testing, data will be thresholded for False Discovery Rates (FDR).

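### IQ is listed as a mediator, but the question the protocol asks about it is effect modification, and the plan has no term for that; visit order for the other mediators is also unstated.

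*Combined protocol and SAP*

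**What the plan says.** The first paragraph of the STATISTICAL PLAN tests Group by Time effects on the cognitive-behavioral measures, with sex, age and education in the models. It then adds that "potential mediating effects of IQ (based on NAART) and pre-test to post-test change in executive function", simple attention, working memory, processing speed and depression "will be explored through covariate mediation modeling". The tests named for these changes (Trails, Color Word Interference, Digit Span, Rey figure, Grooved Pegboard, Beck) are all in the outcome list that opens the paragraph. The IQ test is not.

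Section C.1, Neuropsychological Measures, gives the purpose of each test:

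- The IQ test is the "American National Reading Test (AMNART) for estimated IQ". It was "chosen to determine if changes from treatment could be associated with IQ and to compare groups that may have differential responses to treatment".
- Grooved Pegboard is there partly for "the possibility that improved processing speed might mediate improved retrieval".
- The Beck inventory is there "to determine if mood improvement that may be secondary to HD tDCS application may be accounting for minor improvements in retrieval".

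Follow-up is at 1 week, 3 months and 6 months (Objective #6). Allocation is random, with 80 subjects split equally (General Experimental Approach, item 5).

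**The concern.** A mediator carries an effect because treatment changes it. The pegboard and Beck purposes fit that description. The IQ purpose does not: it asks whether response varies with IQ. The plan analyses IQ as if it were one of the change measures, so a stated question has no matching analysis, and the analysis that is stated has nothing to find.

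For the change measures, the plan refers only to change from pre-test to post-test, although there are three post-treatment visits. Effort, fatigue or practice on a given day can move two tests together. If the mediator and the outcome come from the same day, that shared movement can pass for mediation. At stake is the interpretation: whether a gain in retrieval is specific, or is reported as explained by attention, speed or mood.

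**Working it through.** The documents give no power or effect size for the mediation analysis, so there is no figure of the plan's to reproduce. From the documents: 40 per arm, random allocation, and visits at 1 week, 3 months and 6 months. All effect sizes, slopes and correlations below are assumptions. Simulations used 80 subjects and 4,000 runs, with mediation called when both paths reached two-sided 0.05.

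**IQ as mediator.** The indirect effect is (arm to IQ) × (IQ to outcome), and randomisation makes the first factor zero in expectation.

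- The chance difference in mean IQ between arms has standard error √(2/40) = 0.224 SD.
- With an IQ-outcome slope of 0.3 to 0.5, the noise in the indirect effect is about 0.224 × 0.3 = 0.067 to 0.224 × 0.5 = 0.112 SD.
- Simulated with slope 0.4, the mean indirect effect was 0.00 and mediation was called in 5% of runs.
- When IQ truly modified the effect by 0.5 SD per SD of IQ, the mediation model still averaged 0.00. An arm by IQ test detected the modification in 58% of runs, and gave 4% false positives when there was none.

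**Change measures, if mediator and outcome share a visit.** Let outcome change be Y = tX + e1 and mediator change M = aX + e2, where X is arm, the residuals have unit variance and correlation r, and M has no effect on Y. Regressing Y on X and M gives a coefficient of r for M and a direct effect of t − ra. The false indirect effect is ra, and the false share is ra/t. With t = 0.6 SD:

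| a (SD) | r = 0 | r = 0.2 | r = 0.4 | r = 0.6 |
|---|---|---|---|---|
| 0.6: share (runs calling mediation) | 0% (4%) | 20% (31%) | 40% (73%) | 60% (75%) |
| 0.3: share (runs calling mediation) | 0% (1%) | 10% (11%) | 20% (26%) | 30% (27%) |
| 0: share (runs calling mediation) | 0% (0.3%) | 0% (2%) | 0% (4%) | 0% (5%) |

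When a = t, the share is simply the assumed r. The bias needs both correlated residuals and a stimulation effect on the mediator test.

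**Does ordering the visits solve it?** Take the mediator at 1 week and the outcome at 3 months, with r = 0.4 and a = t = 0.6. The false share falls to 0% if the shared error belongs to the visit. It stays at 40% if it comes from a stable personal trait. Baseline adjustment helps: if all residuals correlate equally at 0.4, the mediator coefficient with p regressors besides arm is 0.4/(1 + (p − 1) × 0.4). Adjusting for baseline mediator and baseline outcome (p = 3) gives 0.4/1.8 = 22%. Adding the 1-week outcome (p = 4) gives 0.4/2.2 = 18%. Neither is zero.

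**Should the 1-week outcome be adjusted for?** Suppose half of a 0.6 SD effect is truly mediated by 1 week (a = 0.6, mediator-to-outcome slope 0.5, direct effect 0.3), and a fraction 0.6 to 1.0 carries forward. The later indirect effect is 0.6 × 0.5 × 0.6 = 0.18 to 0.6 × 0.5 × 1.0 = 0.30 SD. If the later outcome depends on the past only through the 1-week outcome, conditioning on that outcome makes the mediator coefficient zero. True mediation would then be reported as none.

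**The case against.** The strongest reply is that little is exposed. The Group by Time tests come first, mediation is additional and labelled as exploration, and the model without mediators is already the treatment effect. That stands. A reader might infer that a real effect on COWAT or CVLT could be explained away in the efficacy test; the plan does not allow that.

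A reader might also infer that mediator and outcome are taken at the same visits, so the analysis can answer nothing. The documents do not support this. No visits are paired, and the accurate statement is that the order is unspecified. If stimulation leaves a mediator test unchanged, the estimate is correctly near zero. The protocol itself says Digit Span was not chosen as a direct target of stimulation, and that Trails and Color Word are not direct retrieval measures. That points to a smaller than t and so to smaller shares. Nor is it a flaw that these tests are also outcomes: the effect of treatment on a mediator is the first path of any mediation analysis.

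On IQ, the documents say estimated IQ, not a fixed or premorbid trait, and the stated purpose could mean comparing responders with non-responders. Neither point rescues the mediator label. IQ is listed apart from the change measures and is not an outcome, which fits a baseline reading, and comparing responders with non-responders still asks whether response varies with IQ.

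**Conclusion.** The IQ part holds. As written, the analysis has an expected result of zero, with noise of about 0.07 to 0.11 SD under the assumed slopes, and the purpose stated for IQ has no term in the plan. This rests on random allocation and on IQ being a pre-treatment measure.

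The visit-order part holds only conditionally. A false share of ra/t arises if both changes come from one visit and stimulation also moves the mediator test. The tabulated shares, 0% to 60%, illustrate assumed inputs and do not predict this trial's result.

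The point is minor overall. It concerns exploratory interpretation and leaves the COWAT and CVLT efficacy tests untouched.

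**What to change.** **IQ.** Remove IQ from the mediator list. Add an exploratory arm by baseline IQ interaction, with the IQ main effect, on COWAT and CVLT change. State that power is low at 80 subjects: 58% even for the large interaction assumed above, before any FDR adjustment. Use one name for the test, which is AMNART under Neuropsychological Measures and NAART in the STATISTICAL PLAN. The cost is wording plus one more exploratory test per outcome under FDR.

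**Other mediators.**

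- Use change from baseline to 1 week as the mediator, and COWAT and CVLT at 3 and 6 months as outcomes.
- Adjust for baseline mediator and baseline outcome.
- Show results with and without the 1-week outcome; do not adjust for it by default.
- Add a sensitivity analysis for unmeasured mediator-outcome confounding, because ordering the visits does not remove stable shared causes.
- Label the results exploratory.

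**Confirm the schedule.** Objective #6 promises neuropsychological testing at each follow-up, but General Experimental Approach, item 6, names only SORT, COWAT, BNT, CVLT and the ERP tasks. The sponsor should confirm that the mediator tests are given at 1 week. If they are, the change is to SAP text only. If they are not, the lagged analysis would need extra testing at that visit.

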Objective #4: Each subject will undergo a detailed neuropsychological battery to characterize his or her cognitive and behavioral status—including targeted tests that should be affected by improved verbal retrieval, tests of cognitive functions to which the treatment may generalize, and tests consisting of purportedly unrelated functions to account for global, generalized cognitive improvement. They will also undergo pre-treatment EEG (SORT task with EEG, Semantic Selection task with EEG). These will be used as outcome measures for the treatment trial. The two primary outcome measures will be the COWAT and CVLT. Secondary outcome measures will be SORT and Semantic Selection task, performance and ERP for both sets of tasks.

Objective #5: These subjects will then be enrolled in the active treatment aspect of the study. Enrollment of 80 participants is the target for enrollment in the active phase of the treatment trial. Half the subjects will first receive HD tDCS at 1 mA for 20 minutes over the preSMA region for 10 daily sessions (1 session 5 days per week for a 2 week period). The remaining subjects will initially receive sham HD tDCS; after all follow-up evaluations are completed, they will receive the active HD tDCS treatment.

Objective #6: Each subject will receive follow-up neuropsychological and EEG testing at 1 week, 3 months, and 6 months after treatment. This last time point for evaluation extends from our preliminary work showing that later, further improvement in electromodulation treatments can occur at 6 months post-treatment. HD tDCS active treatment subjects enrolled early in the study will be followed longer than 6 months if agreeable to assess length of effect.

Following completion of this clinical trial, we will be able to determine whether HD tDCS is an effective treatment for the verbal retrieval deficits associated with GWI. An HD tDCS cap is a relatively inexpensive piece of equipment that can be re-used many times for multiple patient treatments. These caps are readily available, and the application of the treatment regimen is straightforward to administer. Thus, this treatment can be utilized in any VA medical center or clinic around the nation. In addition, the neuro-psychological tests and ERP/time frequency findings may function as clinical markers for diagnosis and treatment efficacy in subsequent treatment trials to measure treatment response.

SPECIFIC AIMS

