Stage 3. Pre-Treatment Testing. Those meeting criteria of having an established GWI and retrieval deficit will be scheduled for a neuropsychological test battery and EEG testing (SORT task with EEG, Semantic Selection task with EEG) as outlined under *Neuropsychological Measures and EEG Tasks* below. The two primary outcome measures will be the COWAT and CVLT. Secondary outcome measures will be SORT task behavioral and ERP measures, as well as Semantic Selection task performance and ERP measures.

Expected sample sizes. Our target sample of 80 Gulf War veterans who will complete the treatment phase of the study will afford us power to detect a statistically significant difference. Treatment-related change in verbal fluency and memory measures will be the primary outcome measures. Treatment-related change in verbal fluency and memory measures will be the primary outcome measures. A study of the effects of single-session tDCS applied to PFC on verbal fluency measures in normal controls showed a large effect-size, with standardized mean difference Cohen's d = 1.18.²⁰ Additionally, this treatment effect estimate on healthy controls is comparable to or exceeds the effect-size estimates for verbal fluency deficits in GWVs with GWI: Letter Fluency averaging over S1-3 Cohen's d = 0.69; S2 Cohen's d = 1.12, S3 Cohen's d = 0.85; Category Fluency averaging over S1-3 Cohen's d = 0.61, S2 Cohen's d = 0.81, S3 Cohen's d = .61.¹¹ For the treatment effect-size for S2, Cohen's $d = 1.18^{20}$, a sample size of 40 per group yields Power=0.92, and for the deficit effect-sizes for S2, Cohen's d = 1.12, and for S3 Cohen's d = .61, Power =0.94 and Power =0.89, respectively.

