After removing artifacts and segmenting EEG data into multiple trial-by-trial EEG epochs (-200 ms to 1800 ms for SORT and to 1500 ms for SIT), we will apply the STAT-PCA technique that we published, and with which we have longitudinal experience ^{32, 73} for ERP and time frequency data. Baseline corrected ERPs at each space-time (ST) point, and log normalized squared absolute values at each space, time, frequency (STF) point will be calculated and used as input for the inferential stage of STAT-PCA. The statistical model will include the additive effects of group (active vs sham) and time and higher-order additive effects of group, time, and condition (SORT: Bind vs Nonbind; Semantic Selection: Trial-Type [Go vs No-Go] X Categorization [Simple vs. Moderate vs. Complex) on ERP at each space-time point and log power at each STF. Both withinand between-subject variance components will be included. Interaction contrast *t*-statistics for each ERP ST and spectral STF point will be calculated to assess the influence of the interaction terms on log power, and planned t-contrasts will be calculated from condition differences between the groups. Mean differences that survive a threshold of 5% FDR will be stored as a ST and STF arrays and entered into the sequential PCA. For ERP data, the ST array will be put in a matrix in which columns index space and rows index time. For ERP data, PCA will be performed and will return a set of eigenvalues and eigenvectors, which will be subjected to Parallel Analysis ⁷⁴ to determine the number of factors to retain. Only eigenvalues above the 95% confidence intervals of the null distribution will be retained. The retained eigenvectors will be varimax rotated and used to calculate the factor scores by projecting the original dataset onto the eigenvectors. The resulting factor scores will be reshaped such that the columns index electrodes and the rows index time points, and PCA will be performed on this matrix. Factor retention will be determined as in the first sequence. The resulting eigenvectors will represent topographies and their corresponding factor scores will represent the time courses for the interaction effects.

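### STAT-PCA components are built only from arm differences that pass 5% FDR and then applied to the same data, so the size and time course of the ERP treatment effect are biased upward

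*Combined protocol and SAP*

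**What the plan says.** The second paragraph of the Statistical Plan sets out the EEG analysis in a fixed order. Test statistics for the interaction terms are computed at every space-time and space-time-frequency point, and "planned t-contrasts will be calculated from condition differences between the groups". A filter follows: "Mean differences that survive a threshold of 5% FDR will be stored as a ST and STF arrays and entered into the sequential PCA". Parallel Analysis decides how many components to keep. Then: "The retained eigenvectors will be varimax rotated and used to calculate the factor scores by projecting the original dataset onto the eigenvectors". A second PCA is run on the reshaped scores, and the paragraph ends: "The resulting eigenvectors will represent topographies and their corresponding factor scores will represent the time courses for the interaction effects".

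The paragraph names no split sample, no cross-validation, no weights derived without knowledge of arm, and no shrinkage.

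The ERP measures are secondary outcomes, and COWAT and CVLT are primary (Objective #4; Subject Recruitment, Stage 3). Hypotheses 2b and 2c name ERP features beforehand: the 750-ms retrieval versus nonretrieval difference on the SORT, and the Go and NoGo P3 amplitudes. The Statistical Plan has no fixed-window or fixed-electrode analysis for either. The closing paragraph of the Objectives says that the ERP findings "may function as clinical markers for diagnosis and treatment efficacy in subsequent treatment trials".

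**The concern.** The filter is the treatment contrast itself. A point gets through only if its observed arm difference is large, and at 40 per arm a large observed difference is partly chance unless the true one is also large. The component weights therefore lean towards places where chance and effect happened to point the same way. Projecting the same data onto those weights counts that chance again. Differences just under the cut enter as absent, so the cut also shapes the topography.

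This step is the only description of how large the ERP effect is and when it occurs that the plan provides for this secondary outcome. Anyone who takes a magnitude from it, tests the scores, or carries them forward as an efficacy marker carries the bias too.

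**Working it through.** The plan gives no effect size, power or expected number of surviving points for the EEG analysis, so there is no stated figure to reproduce.

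**Inputs from the documents**
- 40 per arm (Expected sample sizes: "a sample size of 40 per group yields Power=0.92"; only the sample size is used here).
- 64 electrodes (EEG Procedure), 512 Hz after down-sampling, and a SORT epoch from −200 to 1800 ms. One SORT ERP map has 64 × (2.0 × 512) = 64 × 1024 = 65,536 points.
- Selection at 5% FDR.

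**Assumed, because the documents are silent:** true d of 0.5, 0.8 and 1.18 (the last is the verbal-fluency effect in Expected sample sizes, used only as a high mark), smooth noise, one focal effect, a 64 × 128 grid (8,192 points), and the Benjamini-Hochberg procedure.

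**Step 1: one point.** The smallest observed difference that can pass a two-sided cut p is d_min = t(1−p/2; 78 df) × √(2/40).
- p < 0.05: 1.991 × 0.2236 = 0.445
- p < 0.005: 2.889 × 0.2236 = 0.646
- p < 0.001: 3.420 × 0.2236 = 0.765

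With noncentrality d × √20, the mean observed |d| among points that pass p < 0.005 is:
- true 0.3: 0.75 (2.5-fold)
- true 0.5: 0.79 (1.6-fold)
- true 0.8: 0.91 (1.13-fold)
- true 1.18: 1.20 (1.02-fold)

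An FDR cut over a whole map can be stricter than any of these. With k survivors among m points, the cut is 0.05 × k/m. For k = 22 and m = 8,192 it is 0.05 × 22/8,192 = 0.00013, and d_min = 4.018 × 0.2236 = 0.90.

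**Step 2: the full sequence, simulated.** Pointwise t, 5% FDR, non-survivors set to zero, first component, projection of all data, peak of the time course. Varimax and Parallel Analysis were left out of Simulation A. It used 250, 200 and 150 runs, of which 18, 70 and 136 had a survivor. Its peaks are projections on a unit-length component, so only the ratio compares with Simulation B, a separate simulation on the same grid that reports SD units.

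| True d | A: peak, same data | A: truth | Ratio | A: peak, independent data | B: peak, same data | B: truth | Ratio |
|---|---|---|---|---|---|---|---|
| 0.5 | 1.42 | 0.54 | 2.6 | 0.58 | 1.01 | 0.41 | 2.5 |
| 0.8 | 1.79 | 1.10 | 1.6 | 1.18 | 1.16 | 0.83 | 1.4 |
| 1.18 | 2.68 | 2.18 | 1.2 | 2.22 | 1.39 | 1.27 | 1.1 |

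At the surviving points in A, the mean absolute difference was 0.93, 0.94 and 0.97 SD against true values of 0.30, 0.56 and 0.78. The ratios are 3.1, 1.7 and 1.2. The apparent size hardly moves while the truth more than doubles.

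**Step 3: no true effect.** In A, any point survived in 14 of 600 runs (2.3%), so the FDR stage kept its error rate. In those 14 runs, testing the component score on the same data gave p < 0.05 every time. In independent data it did so in 1 of 14.

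**Step 4: alternatives.** In B, weights came from simulated pre-treatment data pooled over arms that shared the effect's pattern. The estimates were 0.40 against a true 0.40, 0.63 against 0.64, and 0.95 against 0.94, with 4% false positives. That score detected the effect in 41%, 76% and 99% of runs; the FDR map had any survivor in 12%, 51% and 97%. PCA on the unthresholded difference map was also tried: with no true effect, a same-data test of its score was significant in 97% of maps.

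**The case against.** The strongest reply is that inference comes before the PCA. The contrasts are tested once over all points, and the PCA then summarises what survived. A reader might infer that the FDR procedure fails or that the ERP findings will be false positives. The documents do not support that, and Step 3 shows the error rate holding. A reader might also infer that the plan will report inflated effect sizes or retest the scores. It states neither, so for those uses the bias is a risk and not a planned result. What remains is that the time courses are planned outputs, are not labelled descriptive, and have no unbiased estimate beside them. Preliminary Study #2 also reports a group interaction test on a PCA factor, so a test of component scores is a realistic next step. That earlier PCA is not said to have used thresholded data.

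Second, the dataset that is projected may be the stored group-level array and not participant data, since the matrices described have only space and time dimensions. This does not remove the bias: at d = 0.8 in Simulation A the peak was 1.77 from the stored array and 1.79 from the full data.

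Third, the inflation is slight when the true effect is very large. That stands, so it would be wrong to say that effects are heavily overstated whatever the truth.

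Fourth, components from pre-treatment EEG may capture a feature poorly if it is weak at baseline, and Hypothesis 2b expects the 750-ms difference to be reduced there. That also stands. It limits the power of that option, not its freedom from selection bias, and it is a reason to offer fixed windows as well.

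**Conclusion.** The point holds for magnitude and time course. Under the planned sequence both are biased upward in expectation: roughly 2- to 3-fold for a moderate true effect (d about 0.5) and about 1.1- to 1.2-fold for a very large one (d about 1.2). These factors rest on the assumed smoothness, effect shape, grid and FDR variant. They apply to maps with at least one survivor, and the d = 0.5 row of Simulation A rests on only 18 such maps. The direction follows from the text; the size cannot be derived from it.

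The pointwise FDR decision is sound. Any later test or effect size computed from these factor scores would not be. A reader might extend the point to the trial's main conclusions or suppose that later trials will be sized on these values. COWAT and CVLT are analysed separately and are unaffected, and the Objectives say only that the findings may serve as markers.

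The detection rates in Step 4 favour pre-treatment weights because the simulated baseline shared the effect's pattern. They also compare a test of one score with a whole-map search. With several scores or a poorer match the gain would shrink. This is a cheap improvement, not a flaw that threatens the trial.

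**What to change.** 1. State in the SAP that the FDR map and the STAT-PCA topographies and time courses are descriptive, and that no test or effect size will be computed from those factor scores.
2. Estimate active versus sham, with confidence intervals, on scores whose weights do not depend on the arm contrast, by one of two routes:
   - derive PCA weights from the pre-treatment EEG of all participants pooled over both arms, with arm masked, freeze them, and project each participant's pre-treatment and follow-up EEG onto them; or
   - prespecify electrodes and time windows for the 750-ms SORT difference and the Go and NoGo P3. The preliminary studies already describe a left fronto-temporal site for the former and a frontocentral midline maximum for the latter.
3. Do not replace the thresholded map with an unthresholded one and call the problem solved. Those weights still come from the arm difference, and Step 4 shows that the result is just as circular.

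The cost is SAP wording and a changed order of scripts, with no new data. The downside is that a treatment effect with a topography or latency absent at baseline, or outside the prespecified windows, would appear only in the descriptive map.
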